12.2 Participant demographics and other baseline characteristics

Demographic and other baseline data including disease characteristics will be listed and summarized descriptively for the FAS. In addition, summaries of relevant past or current medical conditions will be presented.

Categorical data will be presented as frequencies and percentages. The summary statistics shown for continuous data will be mean, standard deviation, median, 25th and 75th percentiles, minimum, and maximum.

12.3 Treatments

The Safety set will be used for the analyses of exposure to iptacopan described below.

The duration of exposure (in days) to iptacopan as well as the dose intensity (computed as the ratio of actual cumulative dose received and actual duration of exposure) and the relative dose intensity (computed as the ratio of dose intensity and planned dose intensity) will be summarized by means of descriptive statistics using the safety set.

Concomitant medications and significant non-drug therapies prior to and after the start of the study treatment will be listed and summarized according to the Anatomical Therapeutic Chemical (ATC) classification system.

12.4 Analysis of the primary endpoint(s)/estimand(s)

In the study protocol, 'absence of transfusions' or 'not requiring transfusions' refers to not receiving transfusions and not meeting the criteria for administration of transfusions as per [Section 8.3.2](#).

12.4.1 Definition of primary endpoint(s)/estimand(s)

The primary endpoint related to increase in Hb will define a participant as a responder if

- The change from baseline in hemoglobin is ≥ 2 g/dL on three out of four measurements taken at the visits occurring in last six weeks (from Day 126 to Day 168) of the Core treatment period, and
- The participant has not required (i.e. not received and not met the criteria for administration as per [Section 8.3.2](#)) any packed-red blood cells transfusions between Day 14 and Day 168.
- The baseline hemoglobin will be the mean of the two measurements confirming the hemoglobin entry criterion in participants who do not receive a transfusion between the first and second confirmatory measurements. In participants who receive a transfusion after the first confirmatory measurement, the baseline will be the first measurement.

Intercurrent events stemming from discontinuation of treatment, breakthrough hemolysis events and MAVEs, expected to be reflected in the respective endpoint, will be handled with a treatment policy strategy.

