2.1 Primary estimand

The primary clinical question of interest is:

What is the effect of iptacopan, regardless of discontinuations of study drug or occurrence of BTH or MAVEs, on the primary endpoint (a composite of improvement in hemoglobin levels and absence of RBC transfusions), as assessed by the proportion of responders?

This primary estimand captures both the hematological effect of the study drug (as evaluated by a clinically relevant increase of ≥ 2 g/dL in hemoglobin levels) and the absence of RBC transfusions which are regarded as treatment failure. Further details can be found in [Section 12](#).

The attributes of the primary estimand are:

- Population: PNH Patients ≥ 18 years old with hemolysis (LDH > 1.5 ULN) and anemia (hemoglobin < 10 g/dL), and who have not received any complement inhibitor therapy (including anti-C5 antibody). Further details about the population are provided in [Section 5](#).
- Treatment of interest: the investigational treatment iptacopan at a dose of 200 mg b.i.d regardless of whether the patient discontinues treatment (treatment policy). Further details about the investigational treatment are provided in [Section 6](#).
- Intercurrent events: Transfusions (after Day 14) will be considered treatment failures and as such captured in the endpoint. Discontinuations of study medication for any reason, BTH events, and MAVEs will be handled with a treatment policy strategy.
- The summary measure: the probability of being a responder, standardized to the population of patients assigned to iptacopan in this study.

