Secondary efficacy endpoints include proportion of participants achieving sustained hemoglobin levels \geq 12 g/dL, transfusion avoidance and BTH rates, a PRO measure for fatigue (FACIT-fatigue) as well as changes in reticulocytes and LDH. These endpoints were selected to supplement the primary efficacy endpoint and are clinically meaningful endpoints for PNH. Considering that some patients may present with very low hemoglobin levels (e.g. < 7 g/dL), and thereby require a RBC transfusion during the first two weeks of the Core treatment period, transfusions administered during these first 2 weeks will not be considered for the transfusion avoidance definition.

An extension period of 24 weeks will provide further safety and efficacy data on iptacopan in PNH patients.

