Hepatitis B, C and HIV screen	X													
Physical examination	S		S			S								S
Blood pressure and pulse rate	X		X	X	X	X	X	X	X	X	X	X	X	X
Body height	X													
Body weight	X													X
Body temperature	X		X	X	X	X	X	X	X	X	X	X	X	X
Pregnancy test (serum)	S													
Pregnancy test (urine)			S						S					S
Clinical Chemistry (full)	X		X					X		X				X
Clinical Chemistry (abbreviated)		X(LDH only)		X	X	X	X		X		X	X	X	
Hematology (full) ²	X	X (Hb only)	X	X	X	X	X	X	X	X	X	X	X	X
Coagulation/Markers of thrombosis	X		X			X		X	X	X		X		X

Period	Screening		Core treatment period											
	Visit Name	Screening	Hb /LDH confirm.	Day 1	Day 7	Day 14	Day 28	Day 42	Day 56	Day 84	Day 112	Day 126	Day 140	Day 154
Visit Numbers	1	1	101	102	103	104	105	106	107	108	109	110	111	112
Days	-56 to -1	-56 to -1	1	7 ±1	14 ±1	28 ±1	42 ±3	56 ±3	84 ±3	112 ±3	126 ±3	140 ±3	154 ±3	168 ±3
Weeks	-8 to -1	-8 to -1	1	1	2	4	6	8	12	16	18	20	22	24
Panel of hormones blood samples	X		X			X		X	X	X		X		X
PK blood collection ³				X		X			X					X
DNA sample collection (optional) ⁴			X											
Urinalysis	X		X			X		X	X	X		X		X
Urine Albumin/Creatinine ratio			X						X					X
Breakthrough hemolysis								X						
MAVE								X						
RBC transfusion								X						
12-lead Electrocardiogram (ECG)	X		X						X					X
Adverse Events								X						
Concomitant medications								X						
Surgical and medical procedures								X						
Patient reported outcomes		X ⁵	X	X ⁶	X		X		X		X	X	X	X
Iptacopan DAR								X						
Disposition								X						

X - Assessment to be recorded in the clinical database or received electronically from a vendor

S - Assessment to be recorded in the source documentation only

¹ It is recommended to administer vaccines at least 2 weeks prior to initiation of iptacopan. However, administration of these vaccines less than 2 weeks prior to start of iptacopan or up to 2 weeks (up to Day 14) after iptacopan initiation, is at the discretion of the investigator. If iptacopan treatment is started less than 2 weeks post-vaccination or before a specific vaccination is given, participant must be given prophylactic antibiotic at the start of iptacopan and for at least 2 weeks after vaccination.

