8.3.2 Red blood cell transfusion

The need for administration of RBC transfusion will be monitored continuously during the Core treatment period.

To standardize criteria for administration, transfusion criteria have been established and will apply starting from Day 1 of the study.

Packed-RBC transfusions will be administered to participants in the following cases:

- Hemoglobin level of ≤ 9 g/dL (≤ 8 g/dL for Chinese population) with signs and/or symptoms of sufficient severity to warrant a transfusion
- Hemoglobin of ≤ 7 g/dL (≤ 6 g/dL for Chinese population), regardless of presence of clinical signs and/or symptoms

The level of hemoglobin, the number and unit of transfusion administered as well as the signs and symptoms if applicable will be recorded in the CRFs. Symptoms typically associated with or precipitating participant's need for transfusion are listed below:

- Severe or worsening of fatigue
- Severe or worsening dyspnea / shortness of breath
- Palpitation/angina (or worsening symptoms)
- Change in mental status (syncope, light-headedness, confusion, stroke, transient ischemic attack)

[REDACTED]

The hemoglobin value on which the investigator will base the need of administering a packed-RBC transfusion may be from a local laboratory due to the turnaround time for central lab results. However, the investigator must collect a separate sample for hemoglobin assessment by the central laboratory for analysis at the same time as taking a sample for local lab analysis.

It is recommended that the transfusion is administered within 2-3 days of the assessment of the hemoglobin/event that triggered the requirement. In case the investigator or participant decides not to give or receive a transfusion despite meeting the criteria specified above, the reason should be clearly documented in the CRFs.

During the Extension treatment period, the need for administration of RBC transfusion will be monitored continuously until the end of study visit following the same criteria and guidance described above.

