1.2.1 Primary estimands

The primary clinical question of interest is:

What is the effect of iptacopan, regardless of discontinuations of study drug or occurrence of Breakthrough hemolysis (BTH) or Major Adverse Vascular Events (MAVEs) on the primary endpoint (a composite of improvement in hemoglobin levels and absence of RBC transfusions), as assessed by the proportion of responders?

This primary estimand captures both the hematological effect of the study drug (as evaluated by a clinically relevant increase of ≥ 2 g/dL in hemoglobin levels) and the absence of RBC transfusions after Day 14 which are regarded as treatment failure.

The attributes of the primary estimand are:

- Population: PNH Patients ≥ 18 years old with hemolysis (LDH > 1.5 ULN) and anemia (hemoglobin < 10 g/dL), and who have not received any complement inhibitor therapy (including anti-C5 antibody).
- Treatment of interest: the investigational treatment iptacopan at a dose of 200 mg b.i.d regardless of whether the patient discontinues treatment (treatment policy).
- Intercurrent events: Transfusions (after Day 14) will be considered treatment failures and as such captured in the endpoint. Discontinuations of study medication for any reason, BTH events, and MAVEs will be handled with a treatment policy strategy.
- The summary measure: the probability of being a responder, standardized to the population of patients assigned to iptacopan in this study.

The justification of handling of intercurrent events is in [Table 1-3](#). The overview of estimands and estimation methods is in [Table 5-1](#) in [Section 5.2](#).

Table 1-3 Justification of handling of intercurrent events

Intercurrent event	Handling strategy	Justification
Discontinuation of study medication	Treatment policy	The effect of treatment will be assessed even when participants discontinue study medication. Data collection will be maintained and available measurements post-treatment discontinuation used maintaining the treatment label as assigned at enrollment.
Breakthrough hemolysis events	Treatment policy	The effect of treatment will be assessed. Breakthrough hemolysis may affect the endpoints considered in the study, hence data collection will be maintained and available measurements collected after breakthrough hemolysis event keeping the treatment label as assigned at enrollment.

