2.1.1 General definitions

2.1.1.1 Study day

Study day is defined as the number of days since the date of first dose of study treatment. The date of first dose of study treatment is defined as Day 1 and the day before the first dose of study treatment is defined as Day -1.

Therefore, for a particular date, study day will be calculated as follows:

- for dates on or after the first date of study treatment,
Study day = Assessment date – Date of first dose of study treatment + 1;
- for dates prior to the first date of study treatment,
Study day = Assessment date – Date of first dose of study treatment.

If a patient never took study treatment, one day after the date of completion of screening assessments will be used instead of the date of first dose of study treatment. In that case, one day after the date of completion of screening assessments is defined as Day 1 and the day before the date of completion of screening assessments is defined as Day -1.

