2.5.1 Primary endpoint(s)/Primary estimand(s)

The primary endpoint defines the response as sustained increase in hemoglobin and a participant as a responder if :

- The change from baseline in hemoglobin is ≥ 2 g/dL on three out of four measurements taken at the visits occurring in last six weeks (from Day 126 to Day 168) of the Core treatment period, and
- The participant has not met the criteria for administration of RBC transfusions nor received a transfusion between Day 14 and Day 168.
- The baseline hemoglobin will be the mean of the two measurements taken during screening that confirm the hemoglobin entry criterion in patients who do not receive a transfusion between the first and second confirmatory measurement. In patients who receive a transfusion after the first confirmatory hemoglobin measurement, the baseline will be the first measurement.

Criteria for administration of RBC transfusions

To standardize criteria for administration, transfusion criteria have been established and will apply starting from Day 1 of the study.

Packed-RBC transfusions will be administered to participants in the following cases:

- Hemoglobin level of ≤ 9 g/dL (≤ 8 g/dL for Chinese population) with signs and/or symptoms of sufficient severity to warrant a transfusion
- Hemoglobin of ≤ 7 g/dL (≤ 6 g/dL for Chinese population), regardless of presence of clinical signs and/or symptoms

The transfusions information will be collected on the 'Transfusion-during the study' CRF page.

Handling of intercurrent events of primary estimand

Reaching the protocol established criteria for RBC transfusions will be handled using a composite strategy for primary endpoint.

Intercurrent events stemming from discontinuation of treatment, breakthrough hemolysis events and MAVEs, expected to be reflected in the endpoint, will be handled with a treatment policy strategy.

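### The primary endpoint texts disagree on whether a transfusion, or meeting the transfusion criteria, on Day 14 itself makes a participant a non-responder

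*Protocol*

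**What the plan says.** Three places put Day 14 outside the failure window:

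- Protocol 2.1 (primary estimand): "Transfusions (after Day 14) will be considered treatment failures and as such captured in the endpoint".
- SAP 1.2.1 (primary estimand): the estimand captures "the absence of RBC transfusions after Day 14 which are regarded as treatment failure".
- Protocol 4.1 (rationale): some patients may enter with very low hemoglobin, so "transfusions administered during these first 2 weeks will not be considered for the transfusion avoidance definition". SAP 2.1.1.1 fixes the numbering: "The date of first dose of study treatment is defined as Day 1". The first two weeks are therefore Days 1 to 14.

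The responder definitions put Day 14 inside it:

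- Protocol 12.4.1: the participant must not have required "any packed-red blood cells transfusions between Day 14 and Day 168".
- SAP 2.5.1: "The participant has not met the criteria for administration of RBC transfusions nor received a transfusion between Day 14 and Day 168".
- The same opening day appears in Protocol Table 2-1, in Protocol 12.5.1 and SAP 2.6.1.2 for transfusion avoidance, and in the SAP Table 5-1 footnote. Protocol 4.1 also uses it when it defines a responder, so that section contains both versions.

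Protocol 12.4 and 12.4.1 add that requiring a transfusion means either receiving one or meeting the criteria of Section 8.3.2. Protocol Table 8-1 schedules full hematology at the Day 14 visit, with a window of ±1 day.

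**The concern.** Day 14 is a planned blood draw, so it is one of the days on which the criteria are most likely to be found met. A participant who meets them or is transfused on that day is excused under the estimand and fails under the responder definition. The failure is permanent: it stands whatever the hemoglobin is from Day 126 to Day 168. The same event also decides transfusion avoidance and the hemoglobin ≥12 g/dL response, which carries the same transfusion component.

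The people exposed are those still near the criteria at two weeks, close to the group for whom Protocol 4.1 wrote the grace period. The trial is open-label, so choosing a boundary after such cases are known would be hard to defend.

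**Working it through.** **Does the responder wording include Day 14?** The SAP Table 5-1 footnote uses the same construction for the hemoglobin window, Day 126 to Day 168, and says it holds four scheduled measurements. The scheduled visits are Days 126, 140, 154 and 168. Both ends included gives 4 visits, dropping the first gives 3, and dropping both gives 2. Only the inclusive reading fits the three-of-four rule. Read the same way, the transfusion window includes Day 14.

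**Which cases does the conflict touch?** Take a participant who meets the criteria at the Day 14 visit, held on Day 13, 14 or 15, and is transfused 0 to 3 days later. E is the estimand wording (failure from Day 15). R is the responder wording (failure from Day 14). Both routes to failure are applied.

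| Visit day | Same day | 1 day later | 2 or 3 days later |
|---|---|---|---|
| 13 | excused under E and R | Day 14: excused under E, fails under R | Day 15–16: fails under both |
| 14 | excused under E, fails under R | fails under both | fails under both |
| 15 | fails under both | fails under both | fails under both |

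Two of the 12 combinations depend on the wording. So does a participant who meets the criteria on Day 14 and is never transfused.

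**The plan's own figure.** Protocol 12.8.1 gives a 96.4% probability that the lower bound excludes 15% with N = 40 and a 40% response. It reproduces with the null variance in the critical value:

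Φ[(0.40 − 0.15 − 1.96·√(0.15·0.85/40)) / √(0.40·0.60/40)] = Φ[(0.25 − 0.1107)/0.0775] = Φ(1.80) = 96.4%.

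**Size per participant.** 1/40 = 2.5 percentage points. Expected responders at 40%: 0.40 × 40 = 16. If k of them are lost only through the boundary, the rate is (16 − k)/40, and the same formula gives:

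| k (assumed) | Response rate | Probability of success |
|---|---|---|
| 0 | 40.0% | 96.4% |
| 1 | 37.5% | 93.2% |
| 2 | 35.0% | 88.2% |
| 3 | 32.5% | 80.7% |

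The documents give no value for k.

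**Margin at an observed 16 of 40.** With 12 responders the Wald lower bound is 15.8%. With 11 it is 13.7%, while the percentile-bootstrap bound is exactly 15.0%. An observed 16 could therefore lose four and still pass by either interval.

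**The case against.** Several objections are fair.

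- **The conflict covers one day.** This is correct. Failure for an event on Day 15 is the plan's stated rule, and any fixed cut-off separates neighboring days. Failing regardless of later hemoglobin is the intended composite strategy.
- **Counting Day 14 is conservative.** It can only lower the response rate. That limits the harm, but does not settle which rule defines the estimand.
- **A planned sensitivity analysis helps.** The SAP 2.5.4 analysis based on administered transfusions removes failures from criteria met without a transfusion, including any on Day 14. It leaves a transfusion given on Day 14 unresolved. The local-laboratory and imputed-value analyses do not test the boundary.

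A reader might infer three stronger points that the documents do not support.

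- **A head count.** Suppose entry hemoglobin follows the study-301 inputs of SAP 5.2.2.3 (mean 9.6, SD 1.7 g/dL), truncated below 10, and rises by an assumed 0.5 to 1.0 g/dL by Day 14. Then 5.8% to 2.9% are still at or below 7 g/dL (about 1–2 of 40), and 43.6% to 29.2% at or below 9 g/dL (about 12–17 of 40). These figures describe low hemoglobin at a visit, not misclassified participants. Under this model everyone counted was already under the same threshold at entry, and the criteria apply from Day 1, so earlier transfusions inside the grace period are ignored. The 9 g/dL figure also needs qualifying symptoms, and lower thresholds apply to the Chinese population.
- **A built-in delay past the grace period.** Protocol 8.3.2 says: "It is recommended that the transfusion is administered within 2-3 days of the assessment of the hemoglobin/event that triggered the requirement". That is an upper limit, and same-day or next-day transfusion complies.
- **A need to classify by trigger date or by the Day 14 visit date.** Protocol 8.3.2 does not list a trigger date among the recorded items. Either rule would loosen the primary endpoint in an open-label single-arm trial, and a visit-based boundary would make the grace period vary by participant.

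**Conclusion.** The contradiction is real and sits in current text, within the rule that assigns primary responder status. It is limited to Day 14 itself, for a transfusion received or for criteria met.

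For transfusion avoidance, Protocol 4.1 conflicts directly with Protocol 12.5.1 and SAP 2.6.1.2. For hemoglobin ≥12 g/dL, the secondary estimand text itself opens the window at Day 14, while stating that it considers the same intercurrent events as the primary estimand.

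Neither document says whether actual study day or nominal visit governs the boundary. SAP 2.1.1.1 defines study day by date, but does not tie that to this window.

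Each affected participant costs 2.5 points. The number affected is unknown, and the success probabilities for k = 1 to 3 are illustrations. At a 40% response the trial's conclusion is unlikely to change. The sample size is not in question. The conclusion rests on reading the Day 14 window as inclusive, as the documents do for Days 126 to 168.

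**What to change.** Reconcile the passages to one failure window, stated in actual study days and applied equally to transfusions received and criteria met. Day 15 to Day 168 matches the primary estimand and the two-week rationale.

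Places to align: the Protocol summary, Table 2-1 and Sections 2.1, 2.2, 4.1, 12.4.1 and 12.5.1; SAP Table 1-1, Sections 1.2.1, 1.2.2, 2.5.1, 2.5.2.1, 2.5.3, 2.5.5 and 2.6.1.2, and the Table 5-1 footnote.

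Report the other boundary, with Day 14 included, as a sensitivity analysis for the primary endpoint, hemoglobin ≥12 g/dL and transfusion avoidance. Where the data allow, the same table can show participants whose trigger fell on or before Day 14 but who were transfused after it.

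Do not tie the end of the grace period to the date of the Day 14 visit, and do not make trigger-date attribution the primary rule. The transfusion criteria and patient management do not change. The cost is the wording, one derivation and one table.

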12.4.2 Statistical model, hypothesis, and method of analysis

The primary analysis of the primary endpoint will be a logistic regression to estimate the response probability. The covariates include sex, age (categorical), an indicator variable of baseline hemoglobin above 8 g/dL and an indicator of transfusion dependence at enrollment.

This means that the proportion of responders will be derived from the estimated marginal probabilities derived from the model fit as the mean of the individual logistic regression model predictions, together with the 95% confidence intervals (CI), where the standard error will be derived by the bootstrap method.

The primary analysis of primary endpoint is the assessment of the proportion of patients reaching the status of responder. The lower bound of the two-sided 95% confidence interval of the response rate obtained from primary analysis will be compared to a threshold of 15%. Lower

bound of the two-sided 95% confidence interval $\geq 15\%$ is sufficient for demonstration that iptacopan improves hematological response in PNH patients with hemolysis and anemia in the absence of transfusions. The derivation of the threshold is explained in [Section 12.8.1](#).

